2.2 Patient disposition, demographics and other baseline characteristics

Demographic variables and other baseline characteristics will be summarized for each randomized treatment arm and for all participants based on RAS.

At baseline, the following demographic and baseline characteristics will be summarized:

- Age
- Weight and height
- BMI, and BMI group (<18.5, 18.5 to < 25, 25 to <30, 30 to < 40, >=40)
- Sex (Male vs Female)
- Ethnicity
- Race
- Disease duration (years): date of informed consent - date MDD first diagnosed in Major Depressive Disorder History
- Antidepressants at baseline (ongoing taken during study) in category of
 - Tricyclic Antidepressants (TCAs)
 - Selective Serotonin-Reuptake Inhibitors (SSRIs)
 - Serotonin-Norepinephrine Reuptake Inhibitor (SNRI)
 - Other Antidepressants
- Total number of depressive episodes in history (excluding the current episode): 0, 1-2, 3-5, >5

- Age
- Weight and height
- BMI, and BMI group (<18.5, 18.5 to < 25, 25 to <30, 30 to < 40, >=40)
- Sex (Male vs Female)
- Ethnicity
- Race
- Disease duration (years): date of informed consent - date MDD first diagnosed in Major Depressive Disorder History
- Antidepressants at baseline (ongoing taken during study) in category of
 - Tricyclic Antidepressants (TCAs)
 - Selective Serotonin-Reuptake Inhibitors (SSRIs)
 - Serotonin-Norepinephrine Reuptake Inhibitor (SNRI)
 - Other Antidepressants
- Total number of depressive episodes in history (excluding the current episode): 0, 1-2, 3-5, >5

- Overall severity of current episode (moderate, severity)
- Current major depressive episode features
- Number of hospitalization events for current episode and by category (1, 2, >2)
- Reason for discontinuation of prior MDD treatment failure
- Number of MDD treatment failures (due to lack of efficacy or adverse event), in category of (<2, \geq 2, unknown due to missing)
- Baseline MADRS score
- Baseline MADRS score in category of <30, 30-34, 35-40, >40

Descriptive statistics (n, mean, median, standard deviation, minimum, and maximum) will be presented for continuous variables for each randomized treatment arm and for all participants (total) using RAS. The number and proportion of participants will be presented for categorical variables by treatment arm and all participants (total).

If multiple races have been reported for a participant, the participant will be categorized as multiple races and in each selected race category.

Demographics and baseline characteristics will be listed by treatment arm.

Relevant medical histories and current medical conditions at baseline will be summarized by System Organ Class (SOC) and Preferred Term (PT), by treatment arm.

2.2.1 Patient disposition

Randomized

Participants are considered randomized if they have been assigned a randomization number.

Completing the Core Treatment

Participants are defined as completing the Core Treatment if they have received 3 scheduled infusions in Core Period. It will be derived from Treatment Disposition Form with “Completed” as participant status. Participant who has infusion interruption or skips the second infusion on Day 15 will not be counted as treatment discontinuation if she/he completes the last infusion on Day 29.

Completing the Core Period

Participants are defined as completing the Core Period if they completed the End of Core Visit (Day 43). Participants who discontinue core treatment are encouraged to continue the scheduled visit as indicated in the Assessment Schedule (Protocol Table 8-1).

Eligible for Retreatment in Extension Period

Participants who complete the Core Period on study treatment (with Day 29 infusion completed), and are classified as responders or remitters at the end of Core Period, will be eligible for retreatment with MIJ821 once observe relapse during the Extension Period.

Completing the Retreatment in Extension Period

Participants who are eligible for retreatment and have received 3 scheduled infusions in Extension Period, will be considered as completing the retreatment. It will be derived from Retreatment Disposition Form with “Completed” as participant status. Participant who has infusion interruption or skip the second infusion on Day 15 (Retreatment Period) will not be counted as treatment discontinuation if she/he completes the last infusion on Day 29 (Retreatment Period).

Completing the Extension Period

Participants who are classified as responders or remitters at the end of Core Period will be deemed as completing the Extension Period if they have been observed for 52 weeks in Extension Period or up to clinical worsening after re-treatment, whichever comes first. Participants who are neither responders nor remitters at end of Core Period will be deemed as completing the Extension Period if they have completed the minimum 8 weeks’ safety follow-up in Extension Period.

Participant disposition will be displayed by randomized treatment and overall, in terms of:

- the number and proportion (based on the number of participants within each randomized treatment arm) of participants who receive Core Treatment, complete the Core treatment or discontinue the Core treatment prematurely along with the primary reason, based on RAS
- the number and proportion of participants who completed Core Period or discontinue the Core Period prematurely along with the primary reason, based on RAS
- the number and proportion of responder or remitter at End of Core Visit, as well as the number and proportion of non-responder and non-remitter at End of Core Visit, based on RAS
- the number and proportion of participants who completed the retreatment or discontinued the retreatment prematurely along with the primary reason, based on RTS
- the number and proportion of participants who completed the Extension Period or discontinue the Extension Period prematurely along with the primary reason, based on ENS

In addition, the total number of participants screened, rescreened and screen failed, including the reason for non-inclusion into the study will be provided, based on all screened subjects.

If participants discontinued from study prior to the scheduled visit at 24 hours, the primary efficacy assessment will not be available. Those cases will be flagged along with discontinuation reasons.

The break down of randomization population into each of the analysis sets (see [Section 2.1.3](#)) will be provided in summary table. The exclusion reason from each analysis sets will be listed (see exclusion rule in [Appendix 5.2](#)).

The number of participants with non-pandemic related PDs and pandemic related PDs according to the applicable SOP will be presented. The results of the PDs will be grouped using the broad categories defined in the applicable SOP. A complete list of the PDs can be found in

the Edit Check Specifications document in CREDI. Participants with PDs and non-PDs leading to data exclusion from analysis sets will be listed.

2.3 Treatments (study treatment, rescue medication, concomitant therapies, compliance)

2.3.1 Study treatment / compliance

Descriptive statistics will be produced to describe the exposure to investigational product by treatment arm based on SAF, in terms of:

- the number of participants who received 1, 2 or 3 injections in Core Period. In addition for MIJ821 dose group, the number of injections with active MIJ821 dose will be counted.
- total duration of exposure, calculated by (last injection date – first injection date + 14) days: (for MIJ821 single infusion + 2 subsequent placebo infusions, the last dose date will count placebo infusion as well).

For each visit, the number and proportion of participants receiving study drug will be summarized. The dose change and reason, the duration of each infusion as well as interruption/discontinuation reasons (if applicable) will be listed.

The similar analyses will be provided for retreatment based on Retreatment Set (RTS).

2.3.2 Prior, concomitant and post therapies

For the standardization of data display, concomitant medications and prior medications entered into the database will be coded using the World Health Organization (WHO) Drug Reference List, which employs the Anatomical Therapeutic Chemical classification (ATC) system. Non-drug therapies or procedures will be coded by Medical Dictionary for Regulatory Activities (MedDRA). The data analysis in this section will be based on the coded terminology. Frequency summary (count and proportion) will be provided by ATC (1, 3, 4) and coded name for medications, and by system organ class (SOC) and preferred term (PT) for non-drug therapies.

The missing or incomplete start/stop date of medication/therapy will be imputed before data handling (see imputation rule in [Appendix 5.1.2](#))

Standard of Care

[figure not shown]
Participants must receive pharmacological antidepressant therapy during study. Dosage titration or adjustments of SoC occurring within the first 2 weeks of Core Period are allowed, if needed, with dosages maintained thereafter during the Core period. The SoC includes antidepressant or augmentation, which will be identified by the category of “MDD Related Medications” from CRF form - “Concomitant medication” The SoC during Core Period will be summarized by ATC level (1, 3, 4) and preferred term.

The adjustment of SoC beyond the first 2 weeks potentially may lead to confounding effect to the efficacy assessments over 6 weeks in Core Period. So, any adjustment of SoC post the first 2 weeks will be flagged at individual participant level in listing and the impact on efficacy assessment will be indicated (e.g. adjustment of SoC beyond first 2 weeks in Core Period).

The adjustment of SoC will also not be allowed beyond the first 2 weeks of Retreatment Period. Any adjustments of SoC in Retreatment Period will be flagged similarly in listing but no summary will be provided.

Prohibited Medications and Therapies

The prohibited medications/therapies or those with potential confounding effect for efficacy will be flagged according to [REDACTED]. The impact on efficacy assessments will be evaluated based on the start date/time of taking those prohibited medications/therapies and the protocol deviation report, indicating like “Taken prior to MADRS assessment at 24 hours” “Taken post 24 hours in Core Period” “Taken in Extension Period”. If data warranted, prohibited medications/therapies taken prior to MADRS assessment at 24 hours will be summarized by ATC level (1, 3, 4) and PT for medications, and by SOC and PT for non-drug therapies, and present by listing.

Rescue Medications

The rescue medications could be given to treat agitation, anxiety or aggressive behaviour per investigator judgement or local clinical practice. The recommended rescue medication is

midazolam (maximum dose 2.5 mg orally or intramuscular), any short acting benzodiazepine (e.g. lorazepam), or antipsychotics (e.g. Quetiapin, Olanzapine, Promethazin, or Dipiperon).

The list of rescue medications taken by patient prior to MADRS assessment at 24 hours will be manually reviewed and confirmed via clinical review.

The rescue medication taken prior to MADRS assessment at 24 hours will be flagged in listing as they might have confounding effect to the primary endpoint.

Other Medications and Therapies

The prior MDD related medications and non-MDD related medications will be summarized ATC level (1, 3, 4) and PT.

The prior MDD related non-drug therapies and non-MDD related non-drug therapies including psychotherapy will be presented in listing.

The concomitant MDD related non-drug therapies, and non-MDD related non-drug therapies will be summarized by SOC and PT separately for Core Period and Retreatment Period.

Other non-MDD related concomitant medications will be summarized by ATC level (1, 3, 4) and PT.

2.4 Analysis of the primary objective

The primary clinical question of interest targeting the primary objective is: What is the effect of the MIJ821 versus placebo in change from baseline in MADRS total score at 24 hours post first dose administration, in conjunction with SoC, in patients with MDD who have suicidal ideation with intent, while accounting for intercurrent events with potential confounding effects and intercurrent events leading to study discontinuation prior to the 24 hours assessment.

2.4.1 Primary endpoint(s)/estimand(s)

The primary estimand, defined below, quantifies the treatment effect of MIJ821 at 24 hours post first dose administration while accounting for intercurrent events with potential confounding effects and intercurrent events leading to study discontinuation prior to the 24 hours assessment.

Population: Participants with MDD who have suicidal ideation with intent. All participants included in FAS will be counted.

Variable: Change from baseline in MADRS total score at 24 hours post first dose administration (see definition in [Section 2.4.1.1](#))

Treatment:

There are 6 active MIJ821 dose arms and 1 placebo arm as described in [Section 1.1](#).

- Placebo every other week
- MIJ821 0.0048 mg/kg every other week
- MIJ821 0.016 mg/kg every other week
- MIJ821 0.048 mg/kg every other week

- MIJ821 0.16 mg/kg every other week
- MIJ821 0.048 mg/kg single infusion with two subsequent placebo dosages given every other week
- MIJ821 0.16 mg/kg single infusion with two subsequent placebo dosages given every other week

Since the MADRS total score at 24 hours will be evaluated post the single first injection, treatment arms with different regimens will be grouped into one arm, which turns out to be 4 pooled dose arms and 1 placebo arm during the analysis of this primary estimand:

- Placebo every other week
- MIJ821 0.0048 mg/kg
- MIJ821 0.016 mg/kg
- MIJ821 0.048 mg/kg
- MIJ821 0.16 mg/kg

on top of ongoing pharmacological antidepressant SoC treatment. Dosage titration or adjustments of standard-of-care antidepressant treatment occurred during the first 2 weeks of double-blind treatment are allowed, if needed, with dosages maintained thereafter during the Core Period.

Intercurrent Events (not limited to):

Intercurrent events with potential confounding effect to MADRS assessment at 24-hour:

- Intake or changes in concomitant medications/therapies other than SoC which have potential confounding effects
- Intake of prohibited medications with potential effect
- Intake of rescue medications
- Pandemic related intercurrent events

Participants who took prohibited medications/prohibited therapy treatment or concomitant medications with potential confounding effect and rescue medications will continue to stay in the study. The confounding effect from these medications or therapies will be identified by the approach defined in [Section 2.3.2](#).

Intercurrent events leading to study discontinuation prior to the 24 hour assessment:

- Adverse events (AE)
- Lack of efficacy (LoE)
- Other reasons for study discontinuation

Population Level Summary: Treatment difference of variable means between study drug and placebo

2.4.1.1 Primary endpoint

[figure not shown]
The primary endpoint is the change in MADRS total score from Baseline (Day 1, predose) to 24 hours post first dose in the Core Period. The baseline assessment and the subsequent

[figure not shown]
assessments during study use a 7-day recall period, except that the assessments at 4 hours post dose on dosing day uses a 4-hour recall period, and the assessment at 24 hours post first dose uses a since-last-evaluation recall period.

[figure not shown]
The MADRS consists of 10 items that cover all of the core depressive symptoms (apparent sadness, reported sadness, inner tension, sleep, appetite, concentration, lassitude, interest level, pessimistic thoughts, and suicidal thoughts). For the MADRS performed at 4 hours post dose on Day 1, Day 15 and 25, the MADRS scores for the sleep item and appetite are not recorded and the recorded predose value within the same day will be carried forward. Each item is scored from 0 (item is not present or is normal) to 6 (severe or continuous presence of the symptom). A total score (0 to 60) is calculated by adding the scores of all 10 items. For each item as well as the total score, a higher score represents a more severe condition.

If 2 or more items are missing, no imputation will be performed and the total score will be left missing. Otherwise, the total score will be calculated as the sum of the items present multiplied by the ratio of the maximum possible number of items (i.e., 10) to the number of items present:

Total score = Sum of scores from items present*(10/number of items present)

[figure not shown]

[figure not shown]

2.4.4 Handling of missing values/censoring/discontinuations not related to intercurrent event

For other missing cases which are not caused by intercurrent events defined in [REDACTED], data will be imputed using a MAR mechanism for all treatment arms.

2.4.6 Supportive analyses

MADRS score over visit

Based on FAS, the summary statistics for absolute values and change from baseline of MADRS score by treatment arm (6 dose arms and 1 placebo arm) and analysis visit in Core Period and 2 weeks follow-up in Extension Period, will be provided for the original measurements (i.e. the raw data prior to missing data handling using multiple imputation) of the primary endpoint.

The change from baseline in MADRS score (original measurements) from above visits will also be analyzed using the mixed-effects model for repeated measures (MMRM). This model will include the fixed, categorical effects of treatment, region, time (all analysis visits), and

treatment*time interaction, as well as the continuous, fixed covariates of baseline MADRS score, and baseline MADRS score*time interaction. An unstructured variance-covariance structure will be used to model the within-subject errors. The Kenward-Roger method will be used to adjust the estimated covariance of the mean difference and the degrees of freedom. If the analysis with unstructured covariance structure fails to converge, the compound symmetry will be tested. Model estimated means and their differences of each MIJ821 doses vs. placebo, will be obtained at each timepoint, along with the 90% CI for the difference. Model estimated treatment means in change from baseline in MADRS score (\pm SE) will be plotted over time/visit.

For participants who take retreatment for relapse, the summary statistics for absolute values of MADRS score and change from the baseline of retreatment will be provided in the similar manner, based on RTS. No inferential test analyses will be performed for the retreatment due to limited data.

The individual MADRS scores will be presented in listing.

Individual Item Analyses

Descriptive statistics (n, median, minimum and maximum) will be provided for MADRS item 10 ("Suicidal thoughts") score at baseline and the changes from baseline value at each visit. The treatment difference will be estimated for item 10 using the Hodges-Lehmann estimate, which is the median of all possible paired differences for the change from baseline for individual item. Hodges-Lehmann estimates and the corresponding 90% CI for the treatment differences will be provided for each timepoint.

2.5 Analysis of secondary efficacy objective(s)

There will be no estimand defined for secondary objective(s) in this analysis plan. [REDACTED]

2.5.1 Secondary endpoints

To assess the effect of MIJ821 on sustained response and remission, following secondary efficacy endpoints will be evaluated:

- Proportion of participants meeting response criteria ($\geq 50\%$ reduction from baseline in MADRS total score) over time in the Core Period.
 - Participants who do not meet the criterion or discontinue Core Period prior to the time point due to any reason or with missing score (baseline and/or post baseline) will not be considered as "a responder" at that timepoint.
- Proportion of participants meeting criteria for sustained response ($\geq 50\%$ reduction from baseline in MADRS total score sustained for a period of at least four weeks) in the Core Period

- The sustained response ideally requires all scheduled assessments over four weeks achieving 50% reduction from baseline. However, if there is one or more missing assessment(s) between two responses, the response will be assumed to be sustained over missing assessment(s), unless other specified. For example, one participant observed a response at Day 1 4 hours, Day 29 -2 hours, however missed the assessment at 24 hours, Day 8, Day 15 and Day 22, this participant is still considered as meeting the sustained response. The missing due to study discontinuation will not be imputed. Participants who do not meet the criterion will not be considered as “a responder” at the timepoint.
- Proportion of participants meeting remission criteria (MADRS total score of ≤ 12) over time in Core Period
 - Participants who do not meet the criterion or discontinue prior to the time point due to any reason or with missing score (either at baseline or post baseline) will not be considered as “a remitter” at that timepoint.
- Proportion of participants meeting criteria for sustained remission (MADRS total score of ≤ 12 sustained for a period of at least four weeks) in the Core Period
 - The rule for sustained remission is the similar with sustained response. Participants who do not meet the criterion will not be considered as “a remitter” at the timepoint.
- Proportion of participants meeting criteria for relapse over fixed period in the Extension Period
 - The definition and criteria of relapse could be referred to protocol section 3.4. The relapse will be evaluated by investigator and reported in the CRF form “Relapse and re-treatment criteria”. Participants without relapse reported will not be counted.
- Proportion of relapsing participants meeting response criteria or remission criteria after the first infusion of MIJ821 retreatment in the Extension Period
 - After the retreatment, the proportion of participants meeting response or remission criteria again will be derived based on all relapsing participants who have achieved response or remission at the end of Core Period.

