**Table 6-2 Prohibited medication**

Medication	Prohibition period	Action taken to study treatment***	Reason
Ketamine Esketamine	2 months before Screening and during the whole study duration (Core and Extension)	Discontinue study treatment if in the Core or discontinue study if in the Extension	Safety and PD interaction -additive effects (NMDA receptor antagonists)
Electroconvulsive therapy (ECT), transcranial magnetic stimulation (TMS), Deep brain stimulation (DBS), and Vagus nerve stimulation (VNS)	After Screening and during the whole study duration (Core and Extension)	Discontinue study treatment if in the Core or discontinue the study if in the Extension	PD interaction
Amantadine	After Screening and during the whole study duration (Core and Extension)	Discontinue study treatment if in the Core or Discontinue the study if in the Extension	Safety (CNS additive effects) and PD interaction (weak non-competitive NMDA receptor antagonist)
Monoamine oxidase inhibitors (MAOIs)	14 days before Screening, during the Core, and during the time of relapse retreatment (including 14 days before retreatment)	None	Safety (additive risk of hypertension effect and potential for precipitating hypertensive crisis) and PD interaction
Citalopram and Escitalopram	After Screening, during Core, and during the time of relapse retreatment + 1 week after last MIJ821 dosing	None	Safety (additive risk of QT prolongation, known risk of Torsades de Pointes)
Medications with a "Known Risk of Torsades de Pointes" per www.qtdrugs.org and Table 16-7	7 days before Screening, during Core, and during the time of relapse retreatment + 1 week after last MIJ821 dosing	None	Safety (additive risk of QT prolongation, risk of Torsades de Pointes)
Amitriptyline, Nortriptyline	Within 24 hours prior to each study visit**and up to at least 4 h after end of infusion	None	Safety (additive risk of QT prolongation, risk of Torsades de Pointes)
Quetiapine	Within 12 hours prior to each study visit**and up to at least 4 h after end of infusion	None	Safety (additive risk of QT prolongation, risk of Torsades de Pointes)
Oral and Systemic Hormonal Contraceptives for contraception purposes	After Screening, during Core, and during the time of relapse retreatment+ 1 week after last MIJ821 dosing	None	Not accepted as highly effective contraception method until a dedicated clinical study shows no drug-drug interaction between MIJ821 and hormonal contraceptives

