### 6.2.3 Rescue medication

Rescue medications will not be supplied by the sponsor. The following rescue medications may be considered, and the use of these should be documented in the source documents and the CRFs:

For agitation, anxiety or aggressive behaviour (per investigator judgement or local clinical practice): as required, midazolam (maximum dose 2.5 mg orally or intramuscular), any short acting benzodiazepine (e.g. lorazepam), or antipsychotics (e.g. Quetiapin, Olanzapine, Promethazin, or Dipiperon).

For acute suicidality (e.g. self harm), please refer to [Section 3.2](#) hospitalization, and [Section 10.2.5](#) adverse events of special interest

Prohibited medication (see [Table 6-2](#)) can be administered as rescue medication at any time if clinically warranted.

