  - Post-dose systolic blood pressure of  $\geq 200$  mmHg and/or the DBP is  $\geq 120$  mmHg confirmed by triplicate reading (at least one value should confirm the blood pressure increase above the defined thresholds).

If discontinuation of study treatment occurs, the investigator should make a reasonable effort to understand and record the primary reason for the participant's premature discontinuation of study treatment.

Participants who discontinue study treatment or who decide they do not wish to participate in the study further should NOT be considered withdrawn from the study UNLESS they withdraw their consent (see [Section 9.1.2](#)). Where possible, they should return for the assessments indicated in the Assessment Schedule. If they fail to return for these assessments for unknown reasons, every effort (e.g. telephone, e-mail, letter) should be made to contact the participant/pre-designated contact as specified in the lost to follow-up section.

If the participant cannot or is unwilling to attend any visit(s), the site staff should maintain regular telephone contact with the participant, or with a person pre-designated by the participant. This telephone contact should preferably be done according to the study visit schedule.

Following study treatment discontinuation (no further infusions planned), participants should be followed for two months beyond the 6 week Core Period (Follow-up Period).

Participants who discontinue study treatment during the Core Period should return at every scheduled visit until the End of the 6 week Core Period. The list of assessments should be kept as planned with the following exceptions: ECG and vital signs to be measured (triplicates required), no PK sampling collection, and all assessments that are repeated several times in one day should be done only once [REDACTED]

[REDACTED] Participants will then enter the two months Follow-up Period.

Participants who discontinue study retreatment during the Extension Period should return for the End of Relapse visit and subsequently enter the two month Follow-up Period.

If an onsite visit is not possible, then telephone visits should be conducted and collected at minimum the following:

- New / concomitant treatments
- Adverse Events / Serious Adverse Events

The investigator must also contact the IRT to register the participant's discontinuation from study treatment.

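### In the visible SAP text, MADRS scores obtained after a therapy that ends study treatment in the Core can count as response on the randomised arm

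*SAP*

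**What the plan says.** **Therapies that end study treatment.** For ketamine and esketamine, Protocol Table 6-2 gives the action "Discontinue study treatment if in the Core or discontinue study if in the Extension". ECT, TMS, DBS and VNS carry the same action, and so does amantadine. Protocol 6.2.3 adds that prohibited medication "can be administered as rescue medication at any time if clinically warranted".

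**Follow-up.** Protocol 9.1.1 states: "Participants who discontinue study treatment during the Core Period should return at every scheduled visit until the End of the 6 week Core Period". SAP 2.2.1 defines completion of the Core Period by attendance at the Day 43 visit and treats completion of the Core infusions as a separate item.

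**Response and remission.** SAP 2.5.1 denies responder status at a time point to "Participants who do not meet the criterion or discontinue Core Period prior to the time point due to any reason or with missing score". The matching remission rule opens "Participants who do not meet the criterion or discontinue prior to the time point due to any reason" and then adds missing scores. Sustained response and sustained remission need at least four weeks. Missing visits between two qualifying visits are taken as qualifying.

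**Analysis.** The Core secondary endpoints use the FAS, grouped by randomised arm (SAP 2.1.3 and 2.5.2). SAP Table 5-2 lists no protocol deviation that removes anyone from the FAS. SAP 2.5 defines no secondary estimand, and Protocol 2.2 marks the topic as not applicable.

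**The same events elsewhere.** For the 24-hour primary endpoint, Protocol Table 12-1 discards scores after prohibited therapy and imputes them. After 24 hours, SAP 2.3.2 classifies prohibited therapy by timing. For background antidepressants it says "So, any adjustment of SoC post the first 2 weeks will be flagged at individual participant level in listing", with a note of the effect on the efficacy assessment.

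**The concern.** The secondary objective concerns the effect of MIJ821 on sustained response and remission. A participant given ECT or esketamine in week 1 no longer receives study drug but is still rated weekly. If the MADRS total then falls by at least half, the visible rule records a response for MIJ821 or placebo, although a different treatment may have produced it.

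The rule also separates similar participants by attendance. Someone who leaves the study to have ECT is a non-responder from then on. Someone who has ECT and stays is judged on the score.

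No hypothesis is tested on these endpoints. However, SAP 2.11 names sustained efficacy among the inputs to the interim choice of dose and regimen. Protocol 3.3 then gives the chosen regimen to participants who relapse and have not yet started retreatment.

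**Working it through.** The plan gives no response rate and no rate of prohibited therapy, so it has no figure of its own to reproduce on this point. The check is a trace of the rules, a date calculation and an illustration of size.

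**1. Rule trace, for a participant given ECT on Day 10**
- Table 6-2: study treatment stops; the participant leaves the study only if this happens in the Extension.
- Protocol 9.1.1: visits continue to Day 43.
- SAP 2.2.1: the Day 43 visit is attended, so the Core Period is completed, not discontinued.
- SAP 2.5.1, response: if the score is present and meets the criterion, none of the three exclusions applies. The participant is a responder.
- SAP 2.5.1, remission: *discontinue* has no object. If it means the Core Period, the participant can be a remitter. If it means study treatment, the participant cannot.
- FAS: the result goes to the randomised arm.

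**2. Can such a therapy create a sustained response by itself?** Scheduled visits after Day 2 are Days 8, 15, 22, 29, 36 and 43. Four weeks is 28 days.
- First response at Day 15: 43 − 15 = 28 days. Yes.
- First response at Day 22: 43 − 22 = 21 days. No.
- Using the full ±3-day visit window of Protocol 8: (43 + 3) − (22 − 3) = 46 − 19 = 27 days. Still no.

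So the therapy must start, and response must be seen, by about Day 15. Later therapy, or an antidepressant change after week 2, can only prolong a response that already exists. That includes bridging missing visits under the SAP's rule.

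**3. Size.** Arm size from SAP 3: 27 / 0.9 = 30, and 6 × 30 + 15 = 195, as stated. One participant is 1/30 = 3.3 points, or 1/15 = 6.7 points in the 0.0048 mg/kg arm.

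Let *p* be the response rate without such therapy, *q* the share of the arm who receive it (all otherwise non-responders), and *r* the share of those who then meet the criterion. The observed rate is *p + q × r*, and the arm difference changes by (*q* active − *q* placebo) × *r*. All values below are assumptions: *p* = 30% on placebo and 50% on MIJ821, *r* = 50% to 70%.

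| *q* placebo / active | Placebo rate | Active rate | Difference |
|---|---|---|---|
| 0 / 0 | 30% | 50% | 20 points |
| 10% / 10% | 35–37% | 55–57% | 20 points |
| 10% / 3% | 35–37% | 51.5–52.1% | 16.5–15.1 points |
| 20% / 5% | 40–44% | 52.5–53.5% | 12.5–9.5 points |

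With the imbalance reversed (5% placebo, 10% active) and *r* = 50%, the difference rises by (0.10 − 0.05) × 0.5 = 2.5 points, to 22.5.

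**The case against.** - **Treatment policy is legitimate.** Keeping observed scores on the randomised arm fits the deliberate follow-up in Protocol 9.1.1, and the primary estimand uses that strategy for discontinuations. This stands as a defence of the approach, but not of leaving it undeclared. SAP 2.5.1 is not purely treatment policy either, because leaving the Core already counts as failure. The primary analysis removes scores after these same therapies.
- **Redaction.** Text is blacked out in SAP 2.3.2, 2.5 and 2.5.2, so a rule there cannot be excluded. A reader might infer that the plan has no rule at all; the documents cannot show that. SAP 2.5.3 does send missing-data and discontinuation handling back to 2.5.1, which is visible.
- **Remission may already be covered.** This is a fair reading of the unqualified *discontinue*, and a reason to align the two rules.
- **Low stakes.** No test is planned on these endpoints, and the interim also weighs the 24-hour dose-response, safety and PK. This limits the severity.
- **Stronger readings.** A reader might infer that the rule shrinks the difference from placebo, since lack of effect is a listed reason to stop study treatment. Heavier use in less effective arms is plausible, but the documents give no use by arm, and equal use leaves the difference unchanged. A reader might also infer that everyone who has ECT and stays becomes a responder, or that a late antidepressant change can create a sustained response. The first requires a qualifying score, and the dates rule out the second.

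**Conclusion.** The point holds for per-visit response in the visible text, and may hold for remission. Sustained response is exposed mainly to therapy that starts, and is followed by response, by about Day 15. The same applies to sustained remission if the wording permits. Retreatment endpoints are largely protected, because Protocol 3.2 requires Core completion on study treatment, with the Day 29 infusion, before the 52-week Extension.

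Each qualifying score after such therapy in an otherwise non-responding participant adds 3.3 points to the rate in an arm of 30. The effect on arm differences has no fixed direction. On the assumed rates, a 20-point difference stays at 20 with equal use and falls to roughly 10 to 17 with heavier use on placebo. The primary analysis is unaffected. This is a worthwhile, inexpensive clarification of endpoints that inform the dose and regimen choice.

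**What to change.** In SAP 2.5.1, for the four Core response and remission endpoints, add:

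> From the start of any therapy for which Protocol Table 6-2 requires study treatment to be discontinued in the Core, the participant is counted as a non-responder and non-remitter at all later Core time points. Any period of sustained response or remission ends on that date.

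Also:
- Use the same explicit wording for *discontinue* in the response and remission rules.
- Keep the as-observed (treatment-policy) result as a sensitivity analysis.
- Report the number of affected participants by arm.
- Handle background antidepressant changes after week 2 only in a sensitivity analysis. Limit it to a new or increased antidepressant or augmentation, so that a reduction for tolerability is not scored as failure.

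Referring to the Table 6-2 action, rather than listing therapies, brings in amantadine. The cost is SAP wording, one derivation from therapy start dates that SAP 2.3.2 already uses, and the extra tables. The downside is slightly lower response rates than the as-observed version. Study conduct does not change.
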